#### 3.5 Justification for Placebo as a Control Group

There are no approved treatments for PPD although SSRIs and serotonin and norepinephrine reuptake inhibitors (SNRIs) are commonly used off-label to manage PPD. All subjects whether randomized to the placebo or control group will be allowed to remain on their current antidepressants provided that they have not had a recent change in the medication regimen (for details, please see Section 5.3.2 for prohibited treatments). The add-on design minimizes subject risks because the current medications are not withdrawn, since that could exacerbate depressive symptoms. The duration of the double-blind treatment phase in Cohorts 1-5 of the study is short (60 hours) and is conducted in an inpatient setting, which further minimizes risks to the subjects. The Cohort 6 treatment period is initiated in an inpatient setting, which allows observation of the effects of the IV infusion and first dose effects of the oral medication during the approximately 48-hour stay on the unit.

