# 7.0 STUDY PROCEDURES

This is a Phase 2A, double-blind, placebo-controlled, multiple-dose escalation study consisting of up to 6 cohorts. In Cohorts 1-5 the IV formulation of ganaxolone will be used while in Cohort 6 both IV and oral formulations will be used. Approximately 200 women with PPD 18 to 45 years of age will be screened to randomize approximately 100 subjects across the up to 6 cohorts. Approximately 10-30 subjects will be randomized into each cohort. Randomized subjects will receive ganaxolone or placebo in a 1:1 ratio. In Cohorts 1-5 the treatment is administered intravenously (with or without an initial bolus) over 60 hours. In Cohort 6 the treatment is initiated with a 6-hour intravenous (IV) infusion followed by oral ganaxolone or matching placebo. Additional subjects may be included into these cohorts or additional cohorts may be added, but will not exceed 100 randomized subjects for the study.

The screening period for each cohort will be up to 2 weeks. Following the screening period, there will be a 4-day inpatient treatment phase at a hospital or clinical pharmacology unit for Cohorts 1-5 during which a 60-hour infusion of ganaxolone or placebo will be administered (with or without bolus dosing). The subjects will be discharged from the unit on the morning of Day 4. There will be 2 safety follow-up visits after inpatient discharge on post-treatment Weeks 1 and 4.

[figure not shown]
In Cohort 6, following the screening period, there will be a 1-day inpatient treatment phase at a hospital or clinical pharmacology unit during which a 6-hour infusion of ganaxolone or matching placebo will be administered initially from 9 am to 3 pm ( $\pm$ 1 hour) before oral dosing is started at 7 pm ( $\pm$ 1 hour). The subjects will be admitted on Day 0 and discharged from the unit in the morning of Day 2. The first dose of oral ganaxolone (4 capsules; 900 mg) or matching placebo will be administered at dinner time (around 7 pm) of Day 1, 4 hours after the end of infusion on Day 1. Oral dosing is continued as outpatient on Days 2-28. The dosing regimen during the outpatient phase of Cohort 6 is 900 mg or placebo (4 capsules) at dinner time daily. A 3-day taper will follow at days 29, 30, and 31, as described in Section 3.4.6. There will be 3 safety follow-up visits after the last dose on post-treatment Weeks 1,4, and 6.

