# 7.2 Admission to the Unit (Day 0) – Cohorts 1-6

- Review concomitant medications and therapies
- Admission to the unit. The subject arrives on the unit the day before the start of the infusion (Day 1) to complete assessments and accommodate to the unit.
- Collect vital signs (BP, pulse, temperature, pulse oximetry, respiratory rate)
- Collect ECG
- Collect urine sample for urinalysis, drug screen and urine pregnancy test
- Collect safety laboratory tests
- Collect neurosteroid level
- Measure weight
- CTNI to conduct HAMD17 interview
- Collect AEs
- Conduct CSSRS interview
- Review inclusion and exclusion criteria (including hematology and chemistry from the screening visit); HAMD17 (conducted by CTNI) must be ≥ 22 for randomization.
- Start Q15 minutes health checks (e.g. to observe general wellbeing and behavior, monitor infusion)
- If the subject is breastfeeding, she is encouraged to "pump and dump" while inpatient and for 45 days after the discharged from the unit. She should be provided with a breast pump.

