#### Specific timepoints for assessments on days +1, +2, +3 and +4: - Cohorts 1-5

PK samples: +12h, +24h, +48h, +72h HAMD17: before start of infusion, +12h, +24h, +48h, +60h, +72h all done by CTNI CGI-I: +12h, +24h, +48h, +60h, +72h CGI-S: before start of infusion EPDS: before start of infusion, +60h STAI6: before start of infusion, +12h, +24h, +48h, +60h, +72h ECG: +12h, +24h, +48h, +72h Vital Signs: (BP/P/pO2/RR/Temp): before start of infusion, +4, +8h, +12, +18h, +24h, +32h, +40h, +48h, +56h, +60h, +72h SSS: before start of infusion, +8h, +32h, +56h, +72h CSSRS: before start of infusion, +12h, +36h, +60, +72h Safety laboratory tests and neurosteroid level: +48h Urinalysis drug and pregnancy test: +72h Physical examination: +72h AEs and concomitant medications are collected throughout the inpatient stay.

Q15min health checks are done from the time of admission to the time of discharge. Pulse oximetry (pO2) must be monitored throughout the infusion, including during the night when the subject is sleeping. The subject should be awakened if pulse oximetry falls < 91%.

The following priority order will be in effect when more than 1 assessment is required at a particular time point: 1) HAMD17 2) CGI-I/CGI-S 3) EPDS 4) STAI6 5) SSS 6) CSSRS 7) vital signs 8) ECG 9) safety labs and neurosteroid level 10) PK sample 11) neurosteroid level 12) urinalysis drug screen and pregnancy test 13) physical examination

Day 11 and Day 34 visits have visit windows of  $\pm$  3 and  $\pm$  5 days, respectively

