# 7.5 Infusion (Day +1) – Cohort 6 (Screening and Admission visits for Cohort 6 described in Section 7.1 and 7.2, respectively)

## 7.5.1 **Before Infusion (Morning of Day +1; Baseline)**

- CTNI to conduct HAMD17 interview
- EPDS
- STAI6
- Assess CGI-S
- Review concomitant medications
- Collect vital signs (BP, pulse, temperature, pulse oximetry, respiratory rate),
- Stanford Sleepiness Scale (SSS)
- Conduct CSSRS interview
- Collect AEs
- Randomization
- The subject's bed should be placed close to the nursing station in an area that allows visual observation of the subject
- Start monitoring of pulse oximetry

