## 7.5.2 **During the Infusion and Evening of Day +1 (Day +1)**

- Start 6-hour infusion at 40 mL/hr at 9 am of Day +1 (0h) after baseline assessments are completed (listed above)
- End 6-hour infusion
- Complete +6h assessments after the end of the 6-hour infusion CTNI to conduct interviews for HAMD17 (+6h)
- Conduct interviews for CGI-I (+6h)
- EPDS (+6h)
- STAI6 (+6h)
- Collect AEs
- Collect ECG (+6h)
- Collect VS (BP, pulse, respiratory rate, pulse oximetry, temperature): (+6h)
- Collect SSS (+6h)
- Collect pharmacokinetic samples (+7h [i.e., 1 hour after the end of the infusion], at +10h [i.e., just before the oral dose], and at 1, 2, 3, and 4 hours after the oral dose
- Collect neurosteroid level (+6h)
- Record concomitant medications
- Conduct CSSRS interview (+6h)

CONFIDENTIAL

- Administer the IP: 900 mg of ganaxolone, or matching placebo (four 225 mg capsules or four placebo capsules), at dinner time (i.e., at 7 pm) ±15 minutes of a fatty meal or snack (e.g., fatty yogurt, nuts, avocado)
- Continue monitoring of pulse oximetry and Q15 min health checks

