# 7.7.3 Third Post-treatment Follow-up Visit - 42 days After the Last On-treatment Visit (Day +71)

- The Follow-up Visit 3 should occur about 42 days after the Day 29 visit.
- CTNI to conduct interviews for HAMD17
- Perform EPDS
- Perform STAI6
- Assess CGI-I
- Review concomitant medications and therapies
- Collect vital signs (BP, pulse, temperature, RR)
- Collect urine sample for urinalysis, drug screen and urine pregnancy test
- Measure weight
- Conduct CSSRS interview
- Collect SSS
- Collect AEs

# Table 2. Schedule of Assessments - Cohort 6

Day	Day -14 to -1	Day 0 Admission	Day 1	Day 1 e	Day 2 f	Days 3 & 5	Day 4	Day 8	Days 10 & 13	Day 11	Day 15	Day 22	Day 29	Contraction (Section	17	100 BEA
VISIT	Screenin g		Baseline	Post-BL	Discharge & Outpatient	Safety call	V3 HAMD Call	V4 outpt	0-6-4-	V5 HAMD Call	V6 outpt	V7 outpt	V8 outpt	l st Follow- up	2 nd Follow- up	3 rd Follow- up
Informed consent	X															
Demographics, Medical History	X								10 10							-0
MINI neuropsychiatric interview	X											o				
Inclusion/Exclusion criteria	X	X														
Concomitant Meds and Therapy Review	X	X	X	X	X			X			Х	X	X	X	X	X
Admission to the unit		X														
Discharge from the unit					X			0			2	2 				N
Physical examination	X				X						X		X			
SAFER Interview (during screening)	X															
Vital signs (BP, Pulse, pO2, RR, temp)	X	X	X	X	X			X			Х	Х	X	X	X	X
Height (screening only) and weight	X	X		0.				0	2		X	5	Х	X	Х	X
ECGs	X	X		X	X			x			X	X	x	x		
Safety Laboratory Tests	X	X						x			X		X		X	
Neurosteroid level		X		X	X			X			X	X		X		
Urinalysis, Drug Screen and Pregnancy Tests	X	X		· .				X	2		Х	X	X	X	X	X
CSSRS	X	X	X	X	X			x	· · · ·		X	X	X	X	X	X
Record AEs		X	X	X	X	X		x	X		X	X	X	X	X	x
Randomization			X													
Start infusion (0h; 9 am $\pm$ 1h) a	-	)		X				0	3							0
End infusion (6h)	.a .c.	22		X							0 X0	07.			2	
PK sample collection b				X	X			X			X	X	X	X	1	Ť
HAMD17 c	X	X	X	x	X		x	X		X	X	X	X	X	X	X
CGI-I		)		X	X			X	1997 1997		X	X	X	X	X	X
CGI-S	X	27.	X								0 X0	02				-
EPDS	X		x	X	X			x			x	X	X	X	X	x
SSS			x	X	X			x			X	X	X	X	X	x
STAI6	X	54. 	X	X	X			x	a		x	X	x	X	X	x
Dispense medication/return accountability	a 75	C.Y			X			x	9		x	X	X			
Oral dosing (at dinner time)				X			ť	hroughout	the outpa	tient perio	d	11 75878 G	0.870			
Q15 min health checks & pulse ox d		X	through	out the inpa	tient period			[	•				1			

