Start 3-day taper		i la contra c										64	x			.

a Infusion starts at 9 am and ends 6 hours later at 3 pm and is administered at a constant rate of 40 mL/hr.

b Twelve pharmacokinetic samples are collected in Cohort 6:

On Day 1 subjects will have 6 PK samplings: at 1 hour after the end of the 6-hour infusion (i.e., at 4 pm), at 7 pm (just prior to the oral dosing), and at 1, 2, 3, and 4 hours post oral dosing (at 8, 9, 10, and 11 pm) as well at 8 am the following morning (on Day 2) prior to discharge.

A pharmacokinetic sample is also collected on Days 8, 15, 22, 29, and 36 during the study visit.

c All HAMD17 ratings, except the one done at screening, will be conducted by CTNI raters.

 $^{d}$ Q15min health checks are done from the time of start of the infusion to the time of discharge. Pulse oximetry (pO2) must be monitored from the start of the infusion throughout the inpatient period, including during the night when the subject is sleeping. The subject should be awakened if pulse oximetry falls < 91%.

e On Day +1 all efficacy assessments should be conducted first before lab draws, if possible.

f All Day +2 assessments, including PK and neurosteroid levels, are to be done before the subject is discharged from the unit.

The following priority order will be in effect when more than 1 assessment is required at a particular time point: 1) HAMD17 2) CGI-I/CGI-S 3) EPDS 4) STAI6 5) SSS 6) CSSRS 7) vital signs 8) ECG 9) safety labs and neurosteroid level 10) PK sample 11) neurosteroid level 12) urinalysis drug screen and pregnancy test 13) physical examination

All outpatient visits have  $a \pm 3$ -day visit window, except Visits 3 and 5 which have just  $a \pm 1$ -day visit window and Visits 4 and 6 which have  $a \pm 2$ -day visit window.

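### Cohort 6: Table 2 footnote d starts the 15-minute health checks at the Day 1 infusion, while section 7.2 and the table row it annotates start them at admission on Day 0

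*Protocol*

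**What the plan says.** Protocol section 7.2 lists the Day 0 admission procedures for all six cohorts. One item reads "Start Q15 minutes health checks (e.g. to observe general wellbeing and behavior, monitor infusion".

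Protocol Table 2 is the Cohort 6 schedule. Its row "Q15 min health checks & pulse ox d" is blank at screening, has an X under Day 0 Admission, and then spans the inpatient period. The d in the row label points to footnote d, whose first sentence reads "Q15min health checks are done from the time of start of the infusion to the time of discharge". The rest of footnote d starts continuous oximetry at the infusion. SAP Table 2 reproduces both the row and the footnote.

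Three other places bear on Cohort 6:

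- Section 7.0: "The subjects will be admitted on Day 0 and discharged from the unit in the morning of Day 2".
- Section 7.5.1 (morning of Day 1, before infusion): "Start monitoring of pulse oximetry". It has no item starting the 15-minute checks.
- Section 7.5.2 (infusion and evening of Day 1): "Continue monitoring of pulse oximetry and Q15 min health checks".

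For Cohorts 1-5, the note under Table 1 says "Q15min health checks are done from the time of admission to the time of discharge".

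**The concern.** The two instructions cannot both be followed. Section 7.2 and the X under Day 0 put the start at admission, and the footnote to that same row puts it at the infusion the next morning. Nothing in either document says that a table footnote overrides the procedure section, or the reverse.

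What is at stake is a safety observation in a severely ill group. Inclusion criterion 6 requires a HAMD17 score of at least 26 at screening and at least 22 by the central rater on Day 0. Staff often work from the schedule of assessments. Any who follow footnote d could leave out the checks between admission and infusion, including the night of Day 0, while a site following section 7.2 would carry them out. With about 20 sites planned (section 3.9), practice could differ between sites, and it would be unclear whether an unobserved Day 0 night counts as a protocol deviation.

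**Working it through.** The plan states no figure to reproduce, so the check is a comparison of texts followed by the length of the gap.

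**Where each text starts the Cohort 6 checks**

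| Place | Start of 15-minute checks |
|---|---|
| Protocol 7.2 (Cohorts 1-6) | Admission, Day 0 |
| Protocol Table 2, row | X under Day 0 |
| Protocol 7.5.1 (Day 1, pre-infusion) | No start listed; only oximetry starts |
| Protocol 7.5.2 (Day 1) | Continued, so already running |
| Protocol Table 2, footnote d | Start of infusion, Day 1 |
| SAP Table 2, footnote d | Same as the protocol footnote |
| Protocol Table 1 note (Cohorts 1-5, for comparison) | Admission |

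**Which reading is intended**

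1. Once a Cohort 6 subject is admitted, the only procedure list that starts the checks is section 7.2. If they began on Day 1, section 7.5.1 would be expected to list the start, as it does for oximetry. It does not, and section 7.5.2 uses the language of continuation.
2. The X under Day 0 sits in a row shared by the checks and oximetry. Continuous oximetry starts on Day 1 under both section 7.5.1 and footnote d, and the Day 0 spot reading has its own place in the vital-signs row. The X therefore fits the 15-minute checks best.
3. Section 7.1, also headed for Cohorts 1-6, calls for 15-minute checks on a subject who stays voluntarily on the unit between screening and Day 0. Read literally, footnote d would have her checked before formal admission, unchecked on the night of Day 0, and checked again from the infusion. That is not a plausible design.

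**Size of the gap**

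Inputs: admission on Day 0 and discharge on the morning of Day 2 (section 7.0); infusion at 9 am ± 1 h on Day 1 (section 7.0 and Table 2); four checks per hour.

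- Inpatient nights: Day 0 to 1 and Day 1 to 2, so 2. Footnote d covers only Day 1 to 2, so 1 of 2.
- The documents give no clock time for admission. Assume it falls between 9 am and 5 pm on Day 0.
- Shortest gap: 5 pm on Day 0 to 8 am on Day 1 = 15 h; 15 × 4 = 60 checks.
- Longest gap: 9 am on Day 0 to 10 am on Day 1 = 25 h; 25 × 4 = 100 checks.

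Section 3.5 gives a rough comparison, describing observation "during the approximately 48-hour stay on the unit". From 9 am on Day 1 to the 8 am pre-discharge sample on Day 2 is 23 h, and 48 − 23 = 25 h. The 48 h is approximate, and discharge comes after the 8 am sample, so the 23 h is a minimum and the 25 h an approximate upper figure. It agrees with the long end of the assumed range but does not confirm the whole range.

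**The case against.** The strongest reply is that the documents already settle the matter. Section 7.2 is explicit, section 7.5.2 presupposes that the checks are running, and one footnote sentence is the outlier. On that view this is an editorial slip, and harm requires staff to follow the footnote while ignoring both the X in the row it annotates and the admission list. Two safeguards also remain: subjects with active suicidal ideation are excluded, and the CSSRS is administered on Day 0 and again before the infusion.

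Much of this is fair. The omission is possible rather than certain. The firm size is one night of two, because the hours depend on an assumed admission time. The X under Day 0 is weaker evidence than section 7.2, because its row also covers oximetry. The SAP copy does not direct nursing care, so correcting it is for consistency only.

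What does not stand is that nothing needs to change. The footnote is current text and states an operative rule, and a reader who meets only Table 2 has no means of knowing that it yields to section 7.2. The exclusion criterion and the CSSRS reduce the risk but do not replace the observation that section 7.2 orders. Nor can the checks be treated as infusion monitoring alone, since section 7.2 names general wellbeing and behaviour as well as the infusion.

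A possible cause is that the Amendment 7 summary of changes moves Cohort 6 admission from Day 1 to Day 0, and the footnote would fit the older schedule. This is inference, and the finding does not depend on it.

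**Conclusion.** The concern holds. Footnote d is wrong as written: it contradicts section 7.2, the Day 0 entry in its own row, and the sequence of sections 7.5.1 and 7.5.2. Followed literally, it removes the ordered observation from one of the two Cohort 6 inpatient nights, and that result needs no assumption. The estimate of 15 to 25 hours, or 60 to 100 checks per subject, rests on admission between 9 am and 5 pm. The matter is operational and concerns patient safety. It changes no endpoint, analysis set, analysis or sample size. The Cohort 6 oximetry start and the end of the checks at discharge are consistent across the texts compared here and are not in question.

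**What to change.** Replace the first sentence of footnote d in protocol Table 2 with the wording already used under Table 1, "Q15min health checks are done from the time of admission to the time of discharge", and make the same replacement in SAP Table 2. Leave the Cohort 6 oximetry start where section 7.5.1 and footnote d place it.

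The cost is one sentence in each of two footnotes. Sites take on no new procedure, because section 7.2 already requires the checks from admission.

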## 7.8 Study Evaluations and Procedures

## 7.8.1 **Demographic, Medical History and Other Baseline Characteristics**

Demographic and Other Baseline Characteristics will be collected and recorded on the appropriate sections of the eCRF at the time of the screening visit.

### 7.8.2 **Informed Consent**

The nature of the study and its risks and benefits will be explained to the subject by the principal investigator or designated study personnel. The purpose of placebo control design and the chances of receiving placebo in this study will be discussed with the subject.

### 7.8.3 Eligibility Review

An eligibility review will be conducted by the investigator at the visits specified in Table 1 or 2 using the subject inclusion and exclusion criteria below.

## 7.8.4 **Prior Medication, Concomitant Medication and Concomitant Therapy Review**

At screening, prospective subjects will be asked about medications they have taken in the previous 60 days, including prescription medications, non-prescription medications, vitamins and supplements. At subsequent visits, the subjects will be asked about medications taken since the last visit. During the inpatient treatment phase concomitant medications taken by the subject will be recorded.

The medications that were taken within the past 60 days will be recorded. The medications that were taken within the past 60 days but stopped before the screening visit are recorded on the prior medications eCRF page. The medications that were taken during the study period between the screening visit and last follow-up visit, regardless of whether the medication was started during the study period or before the study period, are recorded on the concomitant medications eCRF page.

The following data will be recorded for all medications used by the subject: drug name, dose, regimen, route of administration, start and stop dates, and the indication for use.

The type of psychological counseling the patient is receiving at the time of screening will be recorded on the Concomitant Psychological Treatment eCRF page.

### 7.8.5 **Physical Examination**

A complete physical examination will be performed at screening, before discharge from the unit, and during visits 6 and 8 (outpatient visits) of Cohort 6.

The physical examination will include a review of the following body systems:

• General appearance

CONFIDENTIAL

- Skin
- Head, Eyes, Ears, Nose, Mouth and Throat
- Neck/Thyroid/Breastfeeding status
- Musculoskeletal
- Respiratory
- Cardiovascular
- Neurological
- Abdomen

The physical examination will be documented in the subject's source documents and on the physical examination eCRF. If a new clinically significant abnormal finding (i.e. not noted at screening) occurs after the screening examination, it must be captured as an AE and documented on the appropriate AE eCRF page.

### 7.8.5.1 12-lead Electrocardiogram

A 12-lead ECG will be conducted at the time points described in Table 1 or 2. Before each measurement the subject should be resting in a supine or semi-recumbent position for 10 minutes. RR, PR, QRS, QTcF and QTcB will be collected. ECGs will be measured with equipment calibrated as per the ECG vendor's standard operating procedure. The ECG results will be assessed by a qualified clinician. The Investigator's assessment of Normal or Abnormal will be recorded and entered in the eCRF page. If a new clinically significant abnormal finding (i.e. not noted at Screening) occurs after the Screening examination, it must be captured as an AE or SAE (if it meets criteria for an SAE – see Section 8.0) and documented on the appropriate AE eCRF page and, if an SAE, submitted to Marinus Safety Department on the SAE form.

7.8.5.2 Clinical Safety Laboratory Evaluations

The name and address of the central clinical laboratory for this study will be maintained in the Investigator's files at each study site.

All clinical laboratory assays will be performed according to the laboratory's normal procedures as described in Table 1 or 2.

Reference ranges are to be supplied by the laboratory and will be used to assess the clinical laboratory data for clinical significance and out-of-range pathological changes. The investigator should assess out-of-range clinical laboratory values for clinical significance, indicating if the values are clinically significant or not. Abnormal clinical laboratory values, which are unexpected or not explained by the subject's clinical condition, may, at the discretion of the investigator or sponsor, be repeated as soon as possible until confirmed, explained, or resolved.

The following clinical laboratory assessments will be performed:

